5.7.2. Start and Stop Dates for Medications

To handle missing/partial dates, the following algorithm will be employed to estimate the time of medication usage relative to study treatment. For start date:

- missing day: impute the 1st of the month unless the same month and year as the study treatment, otherwise impute the first dose date of study drug;
- missing day and month: impute 1st January, unless the same year as the study treatment, otherwise impute the first dose date of study drug.

For stop date:

- missing day: impute the last day of the month unless the same month and year as the study treatment, otherwise impute the last dose date of study drug;
- missing day and month: impute 31st December, unless the same year as the study treatment, otherwise impute the last dose date of study drug.

If any of the above imputations result in a start date that is later than an existing (not imputed) stop date for the event, the start date will be imputed as the stop date. If any of the above imputations result in a stop date that is earlier than an existing (not imputed) start date for the event, the stop date will be imputed as the start date.

5.8. Coding Dictionaries

Medical history and AEs will be coded using the Medical Dictionary for Regulatory Activities (MedDRA). Prior and concomitant medications will be coded using the World Health Organization (WHO) Drug Dictionary.

5.9. Impact of COVID-19

Due to the global Coronavirus Disease 2019 (COVID-19) pandemic and in alignment with guidance put forth by the US Food and Drug Administration (FDA; Conduct of Clinical Trials of

Neurocrine Biosciences, Inc. Statistical Analysis Plan Study NBI-1065846-MDD2020 16August2023

Medical Products During the COVID-19 Public Health Emergency [March 2020, updated January 2021]), Health Canada (Management of Clinical Trials During the COVID-19 Pandemic: Notice to Clinical Trial Sponsors [May 2021]), and European Medicines Agency(EMA; Points to Consider on Implications of Coronavirus Disease [COVID-19] on Methodological Aspects of Ongoing Clinical Trials [March 2020]), the following summaries will be conducted to evaluate the impact of the COVID-19 pandemic, including but not limited to:

- A listing of all subjects affected by the COVID-19 pandemic over the course of study
 participation will be generated. The listing will identify subjects that experience one
 or more of the following situations due to the COVID-19 pandemic (additional
 situations may be included):
 - Discontinued study treatment or withdrew from study
 - Presumed or confirmed diagnosis of COVID-19
 - Had at least one COVID-19 pandemic-related major protocol deviation
 - Missed at least one study visit or assessment
 - Had at least one assessment collected in a non-standard way (eg, remotely)
 - Had at least one study treatment interruption
- A table and/or listing will summarize the COVID-19 pandemic-related reasons for treatment and study discontinuation.
- A table and/or listing will summarize the COVID-19 pandemic-related major protocol deviations.
- A table and/or listing will summarize assessments affected by the COVID-19 pandemic (e.g., missing, partial, collected remotely).

The above listings may be omitted if it is known there was no impact of the COVID-19 pandemic on the study conduct.

Adverse events of diagnosed or presumed COVID-19 infections will be included in the standard summaries of TEAEs and SAEs.

The impact of the COVID-19 pandemic on the primary efficacy endpoint will be evaluated as described in Section 7.4.2.

Neurocrine Biosciences, Inc. Statistical Analysis Plan Study NBI-1065846-MDD2020 16August2023

6. STUDY POPULATION

6.1. Disposition

The summary of subject enrollment and disposition will include:

- The total number of subjects who provided informed consent and were screened
- The following categories will be presented by treatment group and overall. The number of subjects randomized will serve as the denominator to calculate percentages.
 - Randomized subjects
 - Randomized but not treated subjects
 - Completed study treatment
 - Discontinued study treatment prematurely, including reasons for discontinuation.
 - Completed study
 - Discontinued study, including reasons for discontinuation.

A separate summary of randomization by study site will be presented. This summary will display the number of subjects randomized to each treatment group by site.

6.2. Summary of Analysis Sets

A summary of the number and percentage of subjects included in each of the following analysis sets will be provided for each treatment group:

- Full Analysis Set
- Safety Analysis Set
- PK Analysis Set

The number and percentage of subjects excluded from each analysis set by reason for exclusion will also be provided.

6.3. Protocol Deviations

Protocol deviations described in the study-specific Protocol Deviation Plan will be entered into the clinical trial management system. Prior to database lock, all major protocol deviations that have been entered into the clinical trial management system will be exported to a file and integrated into the study data.

Important protocol deviations (IPDs) are protocol deviations that might significantly affect the completeness, accuracy and/or reliability of the study data or that might significantly affect a subject's rights, safety, or well-being. An assessment of IPDs will be performed prior to database lock and unblinding of the randomized treatment assignments. The study team will review a listing of all protocol deviations reported in the study database and determine which deviations are IPDs.

Neurocrine Biosciences, Inc. Statistical Analysis Plan Study NBI-1065846-MDD2020 16August2023

A summary of the number and percentage of subjects with IPDs by deviation category and treatment group will be provided.

All major protocol deviations will be presented in a data listing and any that are classified as IPDs will be flagged in the listing.

The COVID-19 pandemic-related major protocol deviations will be summarized and listed.

6.4. Demographic and Baseline Characteristics

Demographic and baseline characteristics data will be summarized using descriptive statistics for continuous variables, and frequency counts and percentages for categorical variables. Results will be presented by treatment group and overall based on the FAS.

Demographics include:

- Age (years)
- Age groups (<35 years, ≥35 to <50 years, and ≥50 years)
- Sex
- Ethnicity
- Race

Baseline subject characteristics include:

- Height (measured at screening, cm)
- Weight (presented in kilograms)
- Body mass index (BMI; kg/m²)
- HAM-D17 score continuous and categorical (remission [HAM-D17 ≤7], mild illness (HAM-D17 from 8 to 18), and moderate to severe illness [HAM D17 ≥19])
- SHAPS score
- DARS score
- MADRS score
- CGI-S score
- Use of concomitant antidepressant medication(s) (yes, no)
- Use of selective serotonin reuptake inhibitor (SSRI) (yes, no)
- Use of bupropion (yes, no)

6.5. Medical History

Medical history data will be summarized descriptively for the FAS, by treatment group and overall. Medical history data will be coded using MedDRA. The medical history data will be summarized with frequencies and percentages of subjects with at least one medical history item,

Neurocrine Biosciences, Inc. Statistical Analysis Plan Study NBI-1065846-MDD2020 16August2023

and subject frequencies and percentages according to the System Organ Class (SOC) and Preferred Term (PT) levels. The table will be sorted alphabetically by SOC and then, within a SOC, by PT.

Neurocrine Biosciences, Inc. Statistical Analysis Plan Study NBI-1065846-MDD2020 16August2023

7. EFFICACY

The efficacy endpoints and planned analysis methods are described below. Unless otherwise specified, the Full Analysis Set will be used for the primary analyses of all efficacy endpoints. Descriptive statistics will be presented by treatment group according to the study visit. Continuous secondary efficacy endpoints will be analyzed using a similar ANCOVA model as described for the primary endpoint; categorical and ordinal secondary endpoints will be analyzed using the Cochran-Mantel-Haenszel (CMH) Chi-square test adjusted for illness severity (stratification factor) and use of concomitant antidepressant medication(s) at time of randomization.

7.1. Multiple Comparisons and Multiplicity Adjustment

P-values will not be adjusted for multiplicity and should be considered nominal p-values.

7.2. Interim Analysis

There is no planned interim analysis in this study.

7.3. Statistical Hypothesis and Estimand

7.3.1. Statistical Hypothesis

The null hypothesis for the primary endpoint is that the mean change in DARS from baseline to Day 57 in the placebo group is greater than or equal to that in the NBI-1065846 group. The alternative hypothesis is that the mean change in DARS from baseline to Day 57 in the placebo group is less than that in the NBI-1065846 group.

The null hypothesis to be tested is:

$$H_0$$
: $\mu_1 \ge \mu_2$

The alternative hypothesis is:

$$H_1: \mu_1 < \mu_2$$

where μ_1 is the mean change in DARS from baseline to Day 57 in the placebo group, and μ_2 is the mean change in DARS from baseline to Day 57 in the NBI-1065846 group.

7.3.2. Estimand

Consistent with the International Council for Harmonization of Technical Requirements for Pharmaceuticals for Human Use (ICH) E9 Addendum, the 4 attributes of the estimand in conjunction with the primary endpoint are:

- Population:
 - Subjects with a diagnosis of MDD who have been treated with antidepressant medication(s) and who continue to have anhedonia as defined by the study inclusion/exclusion criteria (Section 5 of the protocol).

Neurocrine Biosciences, Inc. Statistical Analysis Plan Study NBI-1065846-MDD2020 16August2023

- Endpoints:
 - Change from baseline in the DARS score at Day 57.
- Intercurrent events:
 - Subjects who discontinue study treatment prematurely or make changes to their background medications will continue to be followed per protocol, therefore the treatment policy strategy will be used to address intercurrent events.
- Summary measures:
 - Difference of means in change from baseline in the DARS score at Day 57 between NBI-1065846 and placebo.

All available assessments up to Day 57 will be used, regardless of occurrence of intercurrent events.

7.4. Primary Efficacy Endpoint

The DARS is a dynamic scale that measures desire, motivation, effort and consummatory pleasure across hedonic domains. The DARS is a self-report questionnaire that measures anhedonia across 4 domains: hobbies/pastimes, food/drinks, social activities, and sensory experiences. The DARS is rated on a five-point Likert scale from 0 (not at all) to 4 (very much), higher values indicating less anhedonia. All items are summed up to a total score in the range of 0 to 68.

Descriptive statistics will be presented by treatment group for the DARS total score observed values, and changes from baseline at each visit. The primary endpoint will be analyzed using the Full Analysis Set by comparing NBI-1065846 and placebo using an Analysis of Covariance (ANCOVA) model. The model will include treatment group, illness severity (stratification factor), use of concomitant antidepressant medication(s) at time of randomization ([ie, yes vs no], covariate), and baseline DARS score (covariate).

Subjects who are missing DARS score at Day 57 will have their data imputed through a multiple imputation (MI) procedure. Missing data will be imputed for subjects in the NBI 1065846 treatment group using retrieved data (i.e., observed data from subjects who discontinued study drug) in that same treatment group, provided there is sufficient retrieved data. Otherwise, missing data will be imputed using observed data from subjects in the placebo treatment group, missing data will be imputed using observed data from subjects in the placebo treatment group. The details of imputation method are described below:

Step 1: For subjects with intermittent missing values, a monotone missingness pattern will be generated by imputing for the intermittent missing values using the Markov Chain Monte Carlo (MCMC) method, which assumes a multivariate normal distribution among all variables included in the imputation model. The MI procedure using SAS® software will be employed for this purpose and this first MI step is planned to be repeated 100 times, creating several different datasets with a monotone missing data structure. The imputation is based on the missing at random (MAR) assumption, i.e., the missing data are assumed to follow the

Neurocrine Biosciences, Inc. Statistical Analysis Plan Study NBI-1065846-MDD2020 16August2023

Status: Approved

same model as the other subjects in their respective treatment arm.

The following SAS® software code will be used to generate the monotone missing data pattern:

Step 2: The remaining missing data will be imputed using a method for monotone missingness based on missing not at random assumption (MNAR). The trajectories of the subjects in the NBI-1065846 treatment group are assumed to follow the retrieved subjects from the same group after the discontinuation, provided there is sufficient retrieved data (the ratio of retrieved data points to the missing data points is greater than 9 to 1[Lee, Huber, 2021]). Otherwise, the trajectories of the subjects are assumed to follow the placebo group after the discontinuation (i.e., control group-based assumption). Thus, for each created dataset with a monotone missing data pattern, the MI procedure using SAS® software will be employed to impute missing DARS total score values based on a sequential procedure reflecting the monotone missing data pattern. Subjects with the first missing value occurring at Day 29 will have their missing Day 29 value replaced by an imputed value from a regression model with treatment group, illness severity, use of concomitant antidepressant medication(s) at time of randomization, and baseline DARS total score as explanatory variables. In the next step, subjects with their Day 57 value missing will have their missing Day 57 value replaced by an imputed value from a regression model with treatment group, the baseline value, and the Day 29 value as explanatory variables.

An example of SAS® software code is provided below to perform the imputation with the MNAR assumption:

Status: Approved

Neurocrine Biosciences, Inc. Statistical Analysis Plan

Study NBI-1065846-MDD2020 16August2023

Step 3: The imputed datasets generated with the approach described above contain only non-missing values and are used as input in the model for the primary analysis after change from baseline values have been calculated at Days 29 and 57. Analysis of covariance model described for the primary analysis will thus be run on each of the 100 generated imputed datasets and the difference between the treatment groups at Day 57 will be estimated. Finally, the MIANALYZE procedure using SAS® software will be applied to combine the results from these analyses to derive an overall estimate of the treatment difference at Day 57. In addition to the estimates, corresponding one sided 90% CIs and p-values will be calculated.

An example of SAS® software code is provided below:

Comparison of NBI-1065846 vs. placebo at each visit will be performed by constructing linear contrasts (or equivalent programming code) for differences between treatment group least-squares (LS) means. The LS means and differences in LS means will be presented in summary tables, along with the associated 90% confidence intervals. The treatment difference for the primary endpoint (Day 57) for NBI-1065846 vs placebo will be considered statistically significant if the one-sided nominal p-value is <0.1. Nominal p-values for comparing treatment groups at the individual postbaseline visits will also be reported in the summary tables.

An example of the SAS® software code for the ANCOVA model is provided below:

Version: 1.0 Status: Approved

Neurocrine Biosciences, Inc. Statistical Analysis Plan Study NBI-1065846-MDD2020 16August2023

To convert the two-sided p-values into one-sided p-value, if the treatment difference for NBI-1065846 vs placebo is in the positive direction, the one-sided p-value equals half of the two-sided p-value; if the treatment difference for NBI-1065846 vs placebo is in the negative direction, the one-sided p-value equals one minus half of the two-sided p-value.

Subgroup analyses for the primary efficacy endpoint will be performed for factors defined in Section 7.6.7 using an ANCOVA model, which will be similar to the model described above for the primary endpoint analysis, including additional fixed factors for the subgroup variable and the interaction between the treatment group and subgroup variable. Nominal two-sided p-values for comparing treatment groups and the associated 95% confidence intervals will be reported in summary tables and a forest plot, and p-values for the interaction term between treatment groups and each subgroup variable will be presented. This study was not designed to detect treatment differences with high statistical power within subgroups. No formal statistical testing will be conducted for subgroup analyses; p-values are nominal and intended to be interpreted in a descriptive manner.

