3.3. Sample Size Considerations

Assuming that 85% of the 88 subjects (randomized in a 1:1 ratio to NBI-1065846 and placebo groups) complete the Day 57 assessment, the study has approximately 80% power to detect an effect size of 0.5 for the primary endpoint at 1-sided significance level of 0.1.

Neurocrine Biosciences, Inc. Statistical Analysis Plan Study NBI-1065846-MDD2020 16August2023

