5.3. Baseline Definition

For efficacy and safety analysis purpose, unless otherwise specified, the assessments collected at the randomization visit (ie, Day1 [Visit 2]) prior to dosing will serve as the baseline value. If the randomization visit value is not available, then the last measurement collected prior to randomization will serve as baseline.

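### The screening DARS, a second pre-randomisation score on the primary scale, is left out of the primary ANCOVA and the imputation regressions; adding it is a cheap option that could sharpen the estimate

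*SAP*

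**What the plan says.** Protocol Appendix A, Table 8 schedules the DARS at screening, Day 1, Day 29, Day 57 and Day 106. Protocol 9.6.2 places randomisation after the Day 1 baseline assessments, so the first two scores precede randomisation as well as dosing.

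SAP 5.3 defines baseline: "the assessments collected at the randomization visit (ie, Day1 [Visit 2]) prior to dosing will serve as the baseline value". An earlier score has one role: "If the randomization visit value is not available, then the last measurement collected prior to randomization will serve as baseline".

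The primary model in SAP 7.4 carries a single DARS term. Besides treatment and the HAM-D17 stratum, it lists "use of concomitant antidepressant medication(s) at time of randomization ([ie, yes vs no], covariate), and baseline DARS score (covariate"). Protocol 11.5.1.2 gives the same list. In Step 2 of the SAP 7.4 imputation, the Day 29 regression uses treatment, illness severity, antidepressant use and baseline DARS. The Day 57 regression uses treatment, baseline and Day 29. Neither uses the screening score.

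On size, SAP 3.3 takes 88 randomised subjects with 85% reaching Day 57 and concludes that "the study has approximately 80% power to detect an effect size of 0.5 for the primary endpoint at 1-sided significance level of 0.1". Neither document gives a DARS standard deviation or correlation, or a reason for leaving the screening score out.

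**The concern.** A single self-report score mixes the subject's stable level with noise specific to that day. A second score taken before randomisation can recover part of the stable level and so explain more of the Day 57 variation. Treatment cannot have affected it, so adjusting for it leaves the estimand unchanged and introduces no bias. A shift in mean between screening and Day 1 does not matter for a covariate.

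With about 75 subjects expected at Day 57, a reduction in residual variance acts like a larger sample, and the data are already scheduled. Only precision is at stake.

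**Working it through.** **1. Reproduce the stated power.** Inputs from SAP 3.3: 88 randomised 1:1, 85% completing, effect size 0.5, one-sided 0.1.

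- Completers: 88 × 0.85 = 74.8, or 37.4 per arm.
- Noncentrality: 0.5 × √(37.4/2) = 2.16, with 72.8 degrees of freedom.
- Power by noncentral t: 80.7% (normal approximation 81.1%). The stated figure of about 80% reproduces.
- The normal approximation needs 37 per arm for 80%, or 74 in total; 74/0.85 = 87.1, which gives 88 at equal allocation.

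**2. Gross effect of a second score.** Let a = corr(Day 1, Day 57), b = corr(screening, Day 57) and c = corr(screening, Day 1).

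- Residual variance with Day 1 only: 1 − a².
- With both scores: 1 − (a² + b² − 2abc)/(1 − c²).
- The gross ratio is the second divided by the first.

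**3. Cost of the extra term.** With N = 75 analysed, the covariates beyond treatment rise from 4 (two for severity, antidepressant use, Day 1 DARS) to 5. Residual degrees of freedom fall from 69 to 68. The expected variance of the treatment estimate is multiplied by (1 + 5/67)/(1 + 4/68) = 1.0149, about +1.5%. The term breaks even when the squared partial correlation of screening with Day 57, given Day 1, is 1 − 1/1.0149 = 0.0147.

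**4. Net result.** The correlations are assumptions. Power takes 0.5 as the effect on the Day-1-adjusted SD, using 0.5/√(net ratio) in the formula of step 1.

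| a / b / c | Gross ratio | Net ratio | Power |
|---|---|---|---|
| Day 1 only | 1 | 1 | 80.7% |
| 0.5 / 0.45 / 0.8 | 0.991 | 1.006 | 80.6% |
| 0.6 / 0.55 / 0.8 | 0.979 | 0.993 | 80.9% |
| 0.5 / 0.45 / 0.7 | 0.974 | 0.988 | 81.1% |
| 0.7 / 0.65 / 0.8 | 0.956 | 0.970 | 81.6% |
| 0.5 / 0.5 / 0.7 | 0.941 | 0.955 | 82.1% |
| 0.6 / 0.6 / 0.75 | 0.920 | 0.933 | 82.7% |
| 0.7 / 0.7 / 0.7 | 0.830 | 0.843 | about 85.5% |
| No added information (b = ac) | 1 | 1.015 | 80.3% |

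Over the grid a = 0.5–0.7, b = a or a − 0.05, c = 0.7–0.8, the net ratio runs from 1.006 to 0.843, with a median of about 0.96. At that median the gain equals about 4 subjects (88/0.96 − 88 = 3.7).

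If b is 0.10 below a, the gain largely disappears: 0.6/0.5/0.75 gives a net ratio of 1.006.

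**5. Simulation of the full ANCOVA** (75 subjects, 12,000 runs per scenario). Variance ratios were 0.90 (all correlations 0.5), 0.87 (all 0.6), 0.99 (0.5/0.45/0.7) and 1.01 (0.6/0.48/0.8, where screening adds nothing). The first two lie outside the grid, because c is below 0.7. One-sided type I error, from 6,000 runs per scenario, stayed between 0.096 and 0.106 across both models, against the nominal 0.1.

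**The case against.** The strongest reply is that nothing here is wrong. The planned ANCOVA already adjusts for the most recent pre-dose score, the stratification factor and antidepressant use, and the stated power is reached without a second score. That stands.

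Three further objections also have force.

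- **The gain is not established.** A reader might infer that the extra covariate would certainly sharpen the estimate. The documents contain no correlation to support that. Screening may precede Day 1 by up to 28 days, extendable by 14, and the Table 8 row for the placebo-control reminder script is marked on Days 1, 29 and 57 but not at screening. Both could weaken the link between screening and Day 57.
- **The study need not be short of power.** A reader might infer that the design has no reserve. SAP 3.3 does not say whether 0.5 is on the raw or the adjusted SD. If raw, Day 1 adjustment alone already gives about 86–96% power for correlations of 0.4–0.7, and the second score adds at most about 3 points.
- **The change goes beyond SAP wording.** The protocol synopsis and Protocol 11.5.1.2 list the covariates too. The imputation regressions may rest on retrieved dropouts or the placebo arm alone, so an extra parameter there has a cost of its own.

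These points limit the claim without removing it: the possible gain exceeds the possible loss, and the data will exist anyway.

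**Conclusion.** The point holds as an efficiency suggestion. A pre-randomisation score on the primary scale goes unused, without explanation, in a valid analysis. Under the assumed correlations, adding it changes the variance of the treatment estimate by between +0.6% and −16%, with a median of about −4%. Power goes from 80.7% to about 80.6–85.5%, provided the 0.5 effect size is on the adjusted SD. In the worst case, where screening adds nothing beyond Day 1, the loss is about 1.5% in variance and 0.4 points of power. The documents do not support reading this as bias, as invalid inference or as a failure of the sample-size calculation.

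**What to change.** Before unblinding, which is when SAP 1 requires analysis decisions to be settled:

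- Add screening DARS as a continuous covariate to the primary ANCOVA and to the Day 29 and Day 57 imputation regressions, so that the imputation and analysis models match.
- Define it as the last score before Day 1 from the screening that led to randomisation, since Protocol 4.1 allows one rescreening and Protocol 9.6.1 allows several screening visits.
- If it is missing, use the Day 1 value.
- Keep change from Day 1 as the endpoint.
- Record the departure from the covariate list in Protocol 11.5.1.2.

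Optionally, confirm the added value first from correlations pooled over arms, still blinded. That check is coarse: break-even is a partial correlation of √0.015 = 0.12, and its standard error with 75 subjects is about 1/√71 = 0.12. If the score is then left out, state why.

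The cost is one degree of freedom in the ANCOVA, one more parameter in each imputation regression, and the documentation.

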7.6.7. Examination of subgroups

The following subgroups will be used to examine consistency of effect for the primary efficacy endpoint:

- Demographics (age groups [<35 years, ≥35 to <50 years, and ≥50 years], sex, and race)
- Baseline HAM-D17 score (≤ 7 vs. 8 to 18 vs. ≥19)
- Baseline HAM-D17 score (<22 vs. ≥22)
- Baseline total MADRS score (≤ 23 vs. 24 to 27 vs. ≥28)
- Baseline MADRS Item 8 score (≤3 vs. ≥4)
- Baseline DARS score (<33th vs. 33th-66th vs. >66th centile)
- Baseline SHAPS score (<41 vs. ≥41)
- Use of antidepressants at baseline (Yes vs. No)
- Use of selective serotonin reuptake inhibitor (SSRI) (yes, no)
- Use of bupropion (yes, no)

Neurocrine Biosciences, Inc. Statistical Analysis Plan Study NBI-1065846-MDD2020 16August2023

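### The Day 57 DARS imputation omits illness severity and antidepressant use, which the Day 29 imputation and the primary ANCOVA include; this can bias the primary estimate modestly, in either direction, under two joint conditions

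*SAP*

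**What the plan says.** All the relevant text is in SAP Section 7.4.

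- **Primary ANCOVA.** "The model will include treatment group, illness severity (stratification factor), use of concomitant antidepressant medication(s) at time of randomization", with baseline DARS as a further covariate. Step 3 runs this model on each imputed dataset.
- **Day 29 imputation (Step 2).** Values are drawn "from a regression model with treatment group, illness severity, use of concomitant antidepressant medication(s) at time of randomization, and baseline DARS total score".
- **Day 57 imputation (Step 2, the following sentence).** Values are drawn "from a regression model with treatment group, the baseline value, and the Day 29 value as explanatory variables".
- **Source of imputed values on NBI-1065846.** Retrieved data from the same arm are used only if "the ratio of retrieved data points to the missing data points is greater than 9 to 1"; otherwise the placebo arm is the source.

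Protocol Section 11.5.1.2 calls for multiple imputation but lists no imputation covariates, so it does not fill the gap. The SAS code announced in SAP 7.4 does not appear in the text available for review, so whether the code carries the two factors cannot be checked.

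**The concern.** An imputation model should contain at least the covariates of the analysis it feeds. Leaving one out amounts to assuming that it has no remaining association with the outcome given what is in the model. Here that assumption is made only at the primary time point, without explanation, and for the sole randomisation stratifier.

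Suppose the assumption fails and one arm loses mainly its more severe subjects. Their missing Day 57 scores are then filled in as if they had the severity mix of the subjects who supply the data. If the other arm does not lose the same mix, the errors do not cancel and the primary treatment difference moves. The test is made at a one-sided level of 0.1 in 88 subjects, so a shift of a fraction of a standard error has a visible effect on the error rate.

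**Working it through.** **1. Planning figure.** SAP 3.3 plans for 88 subjects in two equal arms, with 15% lacking a Day 57 score. On that basis it claims that "the study has approximately 80% power to detect an effect size of 0.5 for the primary endpoint at 1-sided significance level of 0.1". Completers per arm: 88 × 0.85 / 2 = 37.4. Power = Φ(0.5 × √(37.4/2) − 1.282) = Φ(2.162 − 1.282) = Φ(0.880) ≈ 0.81. The stated power reproduces. Planned missing values per arm: 44 × 0.15 = 6.6.

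**2. Which source applies.** With 5 missing in an arm of 44, the rule needs more than 45 retrieved values and at most 39 subjects remain. At the planned 6 to 7 missing, the active arm is therefore imputed from placebo. Both branches are checked below.

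**3. Closed form.** Let β be how far, in SD units, Day 57 DARS is lower in severe subjects at equal baseline and Day 29 DARS. Leaving severity out overstates an arm's mean by

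missing fraction × β × (severe share among the missing − severe share among those supplying the data).

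The shift in the treatment difference is the active value minus the placebo value. As a simplification, the formula treats severity as unrelated to the two DARS scores already in the model.

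Assumptions not in the documents: half the subjects severe; 15% missing per arm; where dropout is severity-related, 25% in one severity group and 5% in the other; β from 0 to 0.6.

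- Arm losing severe subjects (25% severe, 5% milder): severe share of missing 0.125/0.15 = 0.833; of observed 0.375/0.85 = 0.441.
- Arm with the opposite pattern: severe share of missing 0.025/0.15 = 0.167; of observed 0.475/0.85 = 0.559.

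Within-arm imputation:
- Active arm only: 0.15 × (0.833 − 0.441) = 0.059β, so 0.018 to 0.035 SD for β = 0.3 to 0.6.
- Opposite patterns: 2 × 0.059β = 0.118β, so 0.035 to 0.071 SD.
- Same pattern in both arms: 0.059β − 0.059β = 0.

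Placebo-based imputation:
- Active arm only (placebo observed share 0.5): 0.15 × (0.833 − 0.5) = 0.050β, so 0.015 to 0.030 SD.
- Opposite patterns: 0.15 × (0.833 − 0.559) + 0.15 × (0.559 − 0.167) = 0.041β + 0.059β = 0.100β, so 0.030 to 0.060 SD.

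**4. Simulation check.** 88 subjects, true effect 0.5 SD, 15% missing at Day 57, 30% of dropouts also missing Day 29 (assumed), 800 runs, 8 imputations, Rubin's rules. Antidepressant use was given no effect on DARS. Entries are the estimate omitting both factors minus the estimate including them, in SD; Monte Carlo error is about 0.002.

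| Dropout pattern | β | Within-arm | Placebo-based |
|---|---|---|---|
| Opposite by arm | 0 | 0.0018 | −0.0013 |
| Unrelated to severity | 0.3 | 0.0012 | −0.0030 |
| Unrelated to severity | 0.6 | 0.0025 | 0.0006 |
| Same in both arms | 0.3 | −0.0040 | 0.0000 |
| Same in both arms | 0.6 | 0.0011 | 0.0024 |
| Active arm only | 0.3 | 0.0195 | 0.0114 |
| Active arm only | 0.6 | 0.0311 | 0.0312 |
| Opposite by arm | 0.3 | 0.0333 | 0.0302 |
| Opposite by arm | 0.6 | 0.0667 | 0.0608 |

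With both factors included, the within-arm estimate was 0.485 to 0.513 in every scenario. The placebo-based estimate was 0.432 to 0.445, which is the attenuation that method intends.

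**5. What the shift means.** Relative to the planned effect: 0.035/0.5 = 7% and 0.071/0.5 = 14%. Relative to the simulated standard error of about 0.24: 0.035/0.24 = 0.15 and 0.07/0.24 = 0.29. Success is declared on this rule: the difference "will be considered statistically significant if the one-sided nominal p-value is <0.1". If the shift favours the drug, the one-sided error becomes 1 − Φ(1.282 − 0.15) ≈ 0.13 to 1 − Φ(1.282 − 0.29) ≈ 0.16. If the dropout pattern is reversed, the shift works against the drug.

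**The case against.** The strongest reply is that baseline and Day 29 DARS may already carry whatever severity has to say about Day 57 DARS. If so, nothing is lost. A reader might infer that dropout differing by severity and arm is enough to cause bias. It is not: opposite dropout patterns with β = 0 gave a shift of about zero. Protocol Section 2.1 links anhedonia to greater depression severity, but that is not evidence of an effect conditional on two DARS scores. This part of the objection stands, and it makes the point conditional.

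Other defences are weaker.

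- *Parsimony.* The Day 29 step uses both factors, and at planned completion about 37 placebo completers supply the data.
- *Other planned analyses.* The tipping-point analysis (SAP 7.4.1) adds a penalty to the same imputed active values, so it does not restore the covariates. The completers analysis (SAP 7.4.2) uses no imputed values. If it keeps the ANCOVA covariates, it would avoid this particular bias where dropout depends only on stratum and arm. It could expose a discrepancy, but it is supplementary and does not correct the primary estimate.

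Three further inferences go beyond the documents.

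- *Step 1 has the same gap.* Its variable list is not visible, so this cannot be said.
- *The fix would also protect the subgroup results.* Main effects do not preserve treatment-by-subgroup differences, and SAP 7.4 treats those analyses as descriptive.
- *The omission was an oversight.* That is possible, but the text does not show it.

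**Conclusion.** The mismatch in the text is certain; its effect is conditional and modest. Bias needs both a residual effect of severity (or antidepressant use) on Day 57 DARS given baseline and Day 29 DARS, and dropout that depends on that factor differently by arm. If either is absent, the shift is about zero. For severity-related dropout in one arm only, the simulated shift is 0.01 to 0.03 SD. Opposite patterns with a residual effect of 0.3 to 0.6 SD give 0.03 to 0.07 SD. The direction depends on which arm loses the more severe subjects.

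The severity split, dropout rates and residual effects are all assumptions, and opposite patterns by arm are an adverse case rather than an expected one. No magnitude is shown for antidepressant use. This is a worthwhile low-cost correction, not a flaw that undermines the trial.

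**What to change.** In SAP 7.4, Step 2, add illness severity and concomitant antidepressant use at randomisation to the Day 57 imputation regression. It then contains at least the covariates of the primary ANCOVA plus Day 29 DARS. Check that the SAS code matches the revised text. Do both before database lock and unblinding, the point by which SAP Section 1 says analysis decisions are to be made. If the shorter covariate list is deliberate, state the reason instead.

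The cost is about three degrees of freedom in the imputation regression: two for the three-level severity factor and one for antidepressant use. No extra data are needed, since both factors are already required for the ANCOVA.
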